#### 8.4.2 DISEASE RELATED AND ADVERSE EVENT TRACKING

Daily disease related event log and adverse event log forms will be completed. Specific complications common in patients with SAH will be abstracted from the medical record with the date and time of onset and resolution. These include:

- **Seizure:** Electrographic or generalized tonic clonic seizure activity;
- **Cerebral angiography** results and interventions, including the distribution and severity of cerebral vasospasm;
- **Neurologic deteriorations attributable to DCI:** Defined as the development of new focal neurological signs or decreased level of consciousness that resulted in a decrease in the Glasgow Coma Scale (GCS) score of 2 points, lasting at least 1 hour, and not attributable to infection, changes in sedation, or non-ischemic cerebral pathology such as acute hydrocephalus);
- **The need for intervention to manage DCI:** Defined as use of augmented blood pressure goals, cardiac index monitoring, or intra-arterial vasodilator therapy;
- **New onset or previously undocumented myocardial dysfunction:** left ventricular ejection fraction (LVEF)  $\leq$  45%, or a  $>$  10% change from baseline LVEF, LV contractile pattern consistent with neurogenic cardiomyopathy at any measured LVEF, or new wall motion abnormalities;
- **NSTEMI/STEMI:** ST segment changes on 12 lead ECG suspicious for myocardial ischemia, or any elevation of serum troponin above reference range;
- **Hospital acquired infection:** Culture data resulting in the use of antibiotics for  $>$  72 hours;
- **Liver dysfunction:** Liver function tests will be assessed on study day 7. AST or ALT  $>$  3x above baseline values will be identified as an adverse event
- **Thromboembolic events:** Imaging-documented presence of extracranial venous or arterial thrombus.

## 8.5 PHARMACODYNAMIC EFFECT ASSESSMENTS

### 8.5.1 SAMPLE COLLECTION

Blood samples will be collected from study participants after randomization but prior to administration of the first dose of study drug or placebo, and again on study day 7 and study day 10. For patients with an external ventricular drain (EVD), cerebrospinal fluid (CSF) will be collected at each timepoint as well.

10 mL of blood and 5 mL of CSF will be collected at each time point. If the indwelling external ventricular drain is removed prior to study day 10, CSF samples will be collected on the day of planned removal. In the event of inability to collect CSF due to obstructed catheter, or low intracranial CSF volume, one additional attempt will be allowed within a period of 24 hours.

Blood samples will be collected by the bedside nurse and processed for storage by study personnel. CSF samples will be collected by physician medical staff, from external ventricular drainage access, and then processed for storage by study personnel.

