a cerebral aneurysm. An individual who meets any of the following criteria will be excluded from participation in this study: evidence of prolonged QTc >500 milliseconds, baseline AST and ALT > 2x normal reference values, administration of strong inducers/inhibitors of CYP3A4, symptom onset compatible with SAH of  $\geq 3$  days prior to admission to Oregon Health and Science University Neurosciences Intensive Care Unit (OHSU NSICU), unable to speak or understand English or Spanish, current pregnancy based on urine HCG positive pregnancy test, preexisting severe neurologic deficit or condition, chronic renal failure requiring dialysis, severe terminal disease with life expectancy <6 months, or refusal of informed consent.

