We anticipate a possible effect of the study drug in CSF for the following reasons: 1) There is breakdown of the blood brain barrier following SAH and both lipid and non-lipid soluble molecules may be able cross the neurovascular unit due to increased permeability; and 2) Endothelial-derived cytokines and mediators may be transported across compartments, including blood, perivascular space, and CSF. It will be important to confirm the site of action of the study drug is only at the endothelium level or if its effects on the central nervous system

We will collect biomarkers at multiple time points because eicosanoid levels, endothelial dysfunction, and the inflammatory response vary significantly over the natural course of subarachnoid hemorrhage. We may control for significant variations at baseline when interpreting the results.

- **Tertiary Objective:** Provide preliminary estimates of clinically relevant endpoints to inform the design of a larger trial.

We will collect clinical measurements on outcomes throughout the treatment course, at hospital discharge and at 90-day follow-up. To assess DCI directly, we will measure daily middle cerebral artery (MCA) transcranial Doppler flow velocities and the degree of angiographic vasospasm. We will also measure acute changes in neurologic exam, the need for therapeutic interventions for DCI, and new stroke on imaging at discharge. We will also measure more objective surrogate outcomes at hospital discharge and 90-day follow-up including: hospital length of stay, discharge disposition, modified Rankin Scale (mRS), and the extended Glasgow Outcome Scale (GOSE).

**Justification:** This study is not powered to detect an effect of drug administration on these endpoints, but these data will provide information for sample size calculations in larger subsequent studies.

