## 5.2 EXCLUSION CRITERIA

An individual who meets any of the following criteria will be excluded from participation in this study:

- Symptom onset compatible with SAH of > 3 days prior to admission to OHSU

Evidence of QTc prolongation > 500ms on admission  
Baseline AST and ALT > 2x normal reference range  
Administration of any of the following inducers/inhibitors of CYP3A4: ritonavir, indinavir, nelfinavir, saquinavir, clarithromycin, telithromycin, chloramphenicol, ketoconazole, itraconazole, nefazodone, cobicistat or enzalutamide.  
Current pregnancy, based on urine HCG positive pregnancy test  
Preexisting severe neurologic deficit or condition  
Chronic renal failure requiring dialysis  
Severe terminal disease with life expectancy <6 months  
Unable to read or understand written or spoken English or Spanish  
Refusal of informed consent

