## 8 STUDY ASSESSMENTS AND PROCEDURES

### 8.1 SCREENING, CONSENT, AND RANDOMIZATION

**Screening:** Research coordinators will survey the NSICU census on a daily basis to determine which patients are potentially eligible for enrollment. Patients who have cerebral angiography demonstrating ruptured intracranial aneurysm who satisfy the inclusion/exclusion criteria will be approached to provide informed consent. For women of childbearing potential, baseline urine pregnancy test will be performed at admission as part of the standard of care. If not already performed as part of standard medical care, liver function tests will be sent to determine subjects' baseline liver function.

**Consent:** We have developed a written consent to be reviewed and signed by the study participant or surrogate decision making. The recruitment process may take place in-person or by phone. A phone script is attached with this submission. Either the PI, coinvestigators or research staff will explain the objectives, risks and benefits of the study to the patient. We will allow adequate time to answer questions and address concerns.

Some patients will not be able to provide informed consent due to incapacity. Legally authorized surrogate decision makers will be approached to provide consent in these scenarios. There will be no financial compensation or incentive provided to study participants. Study candidates must sign the informed consent form before any study-specific tests or procedures are performed.

**Enrollment/randomization:** Eligible patients are defined as participants meeting all inclusion criteria and none of the exclusions and who have provided a written informed consent. Participants must be screened, consented, and enrolled in the study within 48 hours of admission to the OHSU NSICU. Participants will be randomized as described above. All participants who complete the informed consent process will be assigned a study identification number. Numbers will be assigned in consecutive order starting with the number 100. This number will be followed with another two-digit number representing the randomization sequence starting at 01. Participants will be referenced by the study identification number.

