### 8.4 SAFETY ASSESSMENTS

#### 8.4.1 DAILY ASSESSMENTS

Daily assessments will be performed beginning on the randomization day (day=1), and on subsequent study days that subjects receive study drug (days 2-10). The randomization day will be defined as the time from randomization to the next 6:59 AM. All subsequent study days will be defined as a 24-hour window between 7:00AM and 6:59 AM the following day. Study staff will perform daily assessments from data collected from the medical record as part of patients' routine intensive care unit treatment and monitoring, or by patient interview. These include:

- **Vital Signs:** every four hour vital signs including blood pressure from noninvasive and arterial sources, heart rate, body temperature, and the presence of absence of mechanical ventilation;
- **Cardiac Monitoring:** daily QTc interval, and the presence of cardiac arrhythmias on continuous EKG monitoring.
- **Intake and Output:** total fluids administered and total drain and urine output;
- **Laboratory Assessments:** serum sodium, blood glucose, BUN, creatinine, hematocrit, peripheral white blood cell count;
- **Neurologic Assessments:** GCS, MCA transcranial Doppler velocities and Lindegaard ratios, and headache severity;
- **Concomitant medications:** Daily administration of selected classes of hospital administered concomitant medications will be reviewed for all study subjects during the first 10 days.

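### Day 7 and Day 10 biomarkers are compared with no prespecified adjustment for baseline or time since bleed, although entry can differ by up to 5 days; the cost is precision, not bias

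*Combined protocol and SAP*

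**What the plan says.** **Entry.** Section 5.2 excludes "Symptom onset compatible with SAH of > 3 days prior to admission to OHSU". Section 8.1 adds: "Participants must be screened, consented, and enrolled in the study within 48 hours of admission to the OHSU NSICU". 

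**Clock.** Section 8.4.1 starts daily assessments "beginning on the randomization day (day=1"). It also states: "The randomization day will be defined as the time from randomization to the next 6:59 AM". Later study days run from 07:00 to 06:59.

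**Sampling.** Section 8.5.1 takes blood, and CSF where there is a ventricular drain, after randomisation but before the first dose, "and again on study day 7 and study day 10". If the drain comes out before Day 10, "CSF samples will be collected on the day of planned removal".

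**Biology.** Section 3 says that "eicosanoid levels, endothelial dysfunction, and the inflammatory response vary significantly over the natural course of subarachnoid hemorrhage". Section 4.2 says the same of EETs and gives it as the reason for a placebo group. Section 2.1 places the vascular response in the first 10 to 14 days after the bleed.

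**Existing safeguards.** Section 3 chose the EET/DHET ratio because EET levels fluctuate after the bleed. It also says the team may control for significant baseline variation when interpreting results.

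**Analysis.** Section 9.4.4 compares the arms by two-sample Student's t-test in the per-protocol population, which Section 9.3 limits to patients completing 10 days of drug. It names no covariate. Section 6.3 randomises without restriction or stratification.

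**The concern.** The sampling clock starts at randomisation, whereas the protocol describes the markers as moving with the disease, whose clock starts at the bleed. Patients sampled on the same study day can be at quite different points of the illness. That adds variance to every secondary comparison. With at most 30 patients, unstratified, and fewer among completers and patients with drains, the arms may also differ by chance in mean time since bleed.

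The baseline control mentioned in Section 3 is discretionary and does not reappear in Section 9.4.4. An adjustment for baseline or bleed day chosen after the data are seen would be post hoc, and readers could fairly discount it.

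**Working it through.** The documents give no SD, effect size or power for the pharmacodynamic endpoints (Section 9.2 bases the sample size on safety), so there is no planned figure to reproduce. The timing follows from the documents. Everything after it rests on the assumptions named.

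**1. Time since bleed at each sample.** Onset to admission is 0–3 days (Section 5.2) and admission to enrolment 0–2 days (Section 8.1), so entry is 0–5 days after onset. Let r be the time from randomisation to the next 07:00, 0 < r ≤ 1 day. Study day k then runs from r + (k − 2) to r + (k − 1) days after randomisation.

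- Day 7: 5 to 7 days after randomisation; adding 0–5 gives 5 to 12 days after onset.
- Day 10: 8 to 10 days after randomisation; adding 0–5 gives 8 to 15 days after onset.

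The two ranges overlap from 8 to 12 days. The upper ends are not firm. Section 5.2 counts from admission to the hospital and Section 8.1 from admission to the NSICU, with no stated limit between the two. The synopsis instead excludes onset of 3 days or more, counted as "days prior to admission to Oregon Health and Science University Neurosciences Intensive Care Unit", which gives just under 5 days. These passages should be reconciled.

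**2. Comparisons affected.** Table 1 lists 6 CSF cytokines and 5 blood endothelial markers, analysed as levels: 11 × 2 days = 22. The ratios are serum EET/DHET, CSF EET/DHET and serum EPOME/DPOME: 3 × 2 = 6. So 22 of 28 secondary comparisons are not ratios.

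**3. Chance imbalance between arms.** Two assumptions for the SD of onset-to-randomisation time:

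- uniform on 0–5 days: 5/√12 = 1.44 d;
- two independent uniform windows, 0–3 and 0–2 days: √(9/12 + 4/12) = 1.04 d.

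The SE of the difference in arm means is SD × √(2/n), and the probability of a difference of 1 day or more is 2 × [1 − Φ(1/SE)].

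| n per arm | SD 1.04 d | SD 1.44 d |
|---|---|---|
| 15 | SE 0.38, 0.9% | SE 0.53, 6% |
| 8 (CSF, assumed) | SE 0.52, 5.5% | SE 0.72, 17% |

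**4. Variance explained.** For a linear drift of b residual SDs per day, R² = (b·SD)² / [1 + (b·SD)²].

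| Drift b (assumed) | SD 1.04 d | SD 1.44 d |
|---|---|---|
| 0.2 | 4% | 8% |
| 0.4 | 15% | 25% |

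**5. Effect on the test.** Simulation with 5,000 runs per setting: 15 per arm, entry uniform on 0–5 days, true effect 1 residual SD, two-sided α 0.05. (Section 9.4.4 prints 0.05%, a separate matter.)

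| Drift b | Type I error, t-test | Power, t-test | Power, ANCOVA on time |
|---|---|---|---|
| 0.1 | 0.049 | 0.75 | 0.74 |
| 0.2 | 0.046 | 0.72 | 0.73 |
| 0.3 | 0.055 | 0.68 | 0.74 |
| 0.5 | 0.054 | 0.56 | 0.73 |

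The unadjusted test keeps its level. Adjustment gains nothing at 0.1, about one point at 0.2, and more above that. R² depends only on b × SD, so with the narrower entry SD the 0.2 row corresponds to a drift of about 0.28 (0.2 × 1.44/1.04).

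**The case against.** The case against is substantial, and much of it stands.

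- **Bias.** A reader might infer that mixing disease days biases the comparison or creates false drug effects. The documents do not support that. Time from onset to randomisation is fixed before allocation, so any imbalance is chance, and the t-test already allows for it. The simulated type I error of 0.046 to 0.055 agrees.
- **Variation ignored.** A reader might also infer that the plan overlooks the fluctuation. It does not: the ratio, the concurrent placebo group and the optional baseline control all respond to it. But the ratio rationale is given for EET/DHET only, the placebo group secures validity rather than precision, and the optional control is not specified.
- **Choice of days.** Study-day sampling follows drug exposure: steady state within 6–8 days (Section 2.2) and more than 95% inhibition at 7 days (Section 3). That is a sound reason to keep it. The gap lies in Section 9.4.4, not in the sampling schedule.
- **Missing onset time.** Section 8.2 does not list onset time, and a reader might conclude that it is not recorded. This cannot be settled: the variable list and the schedule of activities are separate attachments, and Section 5.2 cannot be applied without onset.
- **Incomplete remedy.** Time from onset to randomisation does not capture the up to 2 days of spread from the short Day 1 and the within-day sampling window, nor CSF taken early at drain removal. This is correct, and it is why actual sample times should be tabulated as well.

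**Conclusion.** The point holds as a minor matter of precision for secondary endpoints in a phase 1b safety trial. The documents establish the spread (5–12 and 8–15 days after onset), the protocol's own statement that the markers vary over that course, and the absence of any prespecified adjustment for baseline or time since bleed.

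The size of the loss is not established. It depends on the entry-time distribution and the marker drift, and the documents give neither. Over the ranges tried, the loss runs from nothing to a material fall in power (0.73 to 0.56 at the steepest drift with the wider entry spread). At 0.2 SD per day or less the gain from adjusting is negligible. The case for acting is that the change is cheap and has value only if made before the data are seen.

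**What to change.** Keep sampling on study days 7 and 10. In Section 9.4.4:

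1. Prespecify a linear model (ANCOVA) for each Day 7 and Day 10 comparison, with arm, time from symptom onset to randomisation as a linear covariate, and the pre-dose value where available.
2. Report the unadjusted comparison alongside.
3. Tabulate actual onset-to-sample time by arm, identifying CSF taken early at drain removal. Section 8.5.2 already puts date and time of collection on the vials for the eicosanoid samples.
4. Confirm that the onset date and time used for eligibility is kept in the analysis dataset.

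The cost is a short addition to Section 9.4.4, at most one data field that eligibility already requires, and one or two degrees of freedom per model. Onset time will be approximate in some patients, which weakens the covariate but does not bias the comparison, since it is fixed before randomisation.

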### 8.5.2 EICOSANOID PROFILE AND SEH ACTIVITY ASSAY

Samples will be spun down to remove cellular components, and 1mL of the resulting plasma and 2 mL of CSF will be reserved for eicosanoid profile determination. An antioxidant will be added to the plasma and CSF, and these aliquots will be frozen at -80°C in opaque glass vials. Vials will be labeled with the participant ID, type of sample, and date and time of collection. At the end of the enrollment period after the last sample collection, liquid chromatography and mass spectroscopy will be used to determine EET and DHET levels and EPOME and DPOME levels. All samples will be batch processed based on protocols developed and validated by the OHSU Bioanalytical Core Lab.

### 8.5.3 INFLAMMATORY AND ENDOTHELIAL INJURY SAMPLE PROCESSING

The remaining plasma and CSF obtained at each sample collection time point will be frozen at -80°C and reserved for batch processing of the following biomarkers below. Luminex assays for the biomarkers will be processed in the OHSU Anesthesiology Core Lab at the end of the enrollment period after the last sample collection.

TABLE 1: Neuroinflammatory and endothelial injury biomarkers associated with EETs signaling

Biomarker	Role	Blood	CSF
Drug Action			
Eicosanoid Profile (EETs and DHETs)	Drug effect marker[12]	X	X
Inflammatory Biomarkers			
Tumor necrosis factor alpha (TNF-α)	Neuroinflammatory marker, apoptosis, decreased in EETs knockouts[4]		X
Interleukin 1β (IL-1β)	Neuroinflammatory marker[14]		X
Interferon gamma (IFN-γ)	Neuroinflammatory marker, decreased in sEH knockouts[4]		X
Interleukin 6 (IL-6)	Neuroinflammatory marker, associated with vasospasm,[14] decreased in sEH knockouts[4]		X
Interleukin 8 (IL-8)	Neuroinflammatory marker, associated with vasospasm[14]		X
Monocyte chemoattractant protein 1 (MCP-1)	Neuroinflammatory marker, associated with vasospasm[14]		X
Endothelial Injury			
e-selectin	Leukocyte adhesion marker[15]	X	
p-selectin	Platelet adhesion marker[16]	X	
Vascular cell adhesion marker (VCAM-1)	Vascular inflammation, blood brain barrier breakdown, hydrocephalus[17]	X	
Platelet endothelial cell adhesion marker (PECAM-1, CD31)	Leukocyte, platelet, monocyte adhesion, angiogenesis[16]	X	
Intercellular adhesion molecule (ICAM-1)	Endothelial surface marker for inflammation [16]	X	

### 8.5.4 EPHX2 POLYMORPHISM ANALYSIS SAMPLE PROCESSING

sEH activity variation as a result of genetic polymorphisms of EPHX2 have the potential to exist in the study population and act as confounders. We will determine sEH EPHX2 genotype at the end of the enrollment period after the last sample collection. DNA will be extracted and purified from peripheral leukocytes isolated from collected blood samples. Allelic discrimination of

EPHX2 will be performed by TaqMan amplification and quantitative PCR (qPCR). We will use probes for 2 of the most common EPHX2 genotypes, K55R and R287Q, as these are the most common and demonstrated to have a clinical effect in patients with SAH. We have previously validated this method with DNA sequencing.

## TERTIARY ENDPOINT ASSESSMENTS

### **Discharge and Follow-up Assessments:**

At hospital discharge and 90-day follow-up, we will also measure objective clinical surrogate endpoints. The hospital discharge assessment will be abstracted from the patient medical record and obtained from patient interview. The 90-day follow-up assessment will be obtained from phone interview with the patient or their surrogate. We will collect the following information:

- **At Hospital Discharge:**
  - **Hospital length of stay**, in days
  - **New stroke on imaging:** We will review the last head CT or other brain imaging to detect the presence of a new area of cerebral infarction. We will define a cerebral infarction identified on hospital discharge that was not present on imaging between 24–48 hours after aneurysm occlusion, and not attributable to other causes such as surgical clipping or endovascular treatment. Hypodensities resulting from extraventricular drains or residual intraparenchymal hematomas will not be considered new strokes.
  - **Discharge disposition:** We will record the disposition from the hospital in one of the following categories: home, home with services, rehab, LTAC, SNF, hospice, death
  - **Modified Rankin Scale:** We will determine and record the mRS score from where 0 – no symptoms, 1 – no significant disability, able to carry out all usual activities despite some symptoms, 2 – slight disability. Able to look after own affairs without assistance, but unable to carry out all previous activities, 3 – moderate disability, requires some help, but able to walk unassisted, 4 – moderately severe disability, unable to attend to own bodily needs without assistance, and unable to walk unassisted, 5 – severe disability, requires constant nursing care and attention, bedridden, incontinent, 6 – deceased.
- **At 90-day follow up**
  - **Modified Rankin Scale**
  - **Extended Glasgow Outcome Scale (GOSE):** At 90 day follow up, we will determine the GOSE based on a structured interview of 19 questions detailed in the variable list and assessment tools. We will record the GOSE on a scale of 1-8 where 1 – deceased, 2 – vegetative state, 3 – low severe disability, 4 – upper severe disability, 5 – low moderate disability, 6 –upper moderate disability, 7 – low good recovery, 8 – upper good recovery.

